11.2. Access to Data

The CI, PIs and all institutions involved in the trial will permit trial related-monitoring, audits, REC review, and regulatory inspection. In the event of an audit, the CI will allow the Sponsor, representatives of the Sponsor or regulatory authorities direct access to all trial records and source documentation.

11.3. Archiving

Archiving of trial documents will be as detailed in the archiving plan, in compliance with Sponsor SOPs. All trial documentation, electronic and paper, will be kept for 25 years. Medical records will be maintained in compliance with local NHS policy on retention of medical records. The Sponsor will be responsible for archiving the Trial Master and Sponsor File, sites will be responsible for archiving local trial records including the Investigator Site File (ISF) and Pharmacy Site File.

12. MONITORING, AUDIT & INSPECTION

12.1. Monitoring

A trial risk assessment will be carried out by the Sponsor prior to Sponsorship approval being granted. The Sponsor has determined the appropriate extent and nature of monitoring for the trial and will appoint appropriately qualified and trained monitors independent to the trial team. A Monitoring Plan will be developed by the sponsor based on the trial risk assessment which may include on site monitoring. The Monitoring Plan will be reviewed regularly using a risk-based approach and up-dated as required. The Monitoring Plan will detail the procedures and anticipated frequency of monitoring, processes reviewed. It is anticipated that due to the COVID-19 pandemic that monitoring will be completed remotely. Sites must have access to source data for purposes of remote monitoring and assist the Sponsor in monitoring of the trial. In recognition that source data may come from different sources at each site, sites shall ensure that a source data identification list is supplied to the Monitoring Team in advance of any monitoring review and ensure they have this data is available on the agreed date and time to facilitate the review

13. ETHICAL AND REGULATORY CONSIDERATIONS

13.1. Research Ethics Committee review & reports

Before the start of the trial, approval will be sought from Scotland A REC (approved to review trials requiring ethical approval under the Adults with Incapacity (Scotland) Act 2000) for the trial protocol, ICF and other relevant documents, e.g. GP information letters

Substantial amendments that require review by REC will not be implemented until the REC grants a favourable opinion for the trial.

All correspondence with the REC will be retained in the TMF.

An annual progress report will be submitted to the REC within 30 days of the anniversary date on which the favourable opinion was given, and annually until the trial is declared ended. It is the Cl's responsibility to produce the annual reports as required.

The CI will notify the REC of the end of the trial. If the trial is ended prematurely, the CI will notify the REC, including the reasons for the premature termination. Within one year after the end of the trial, the CI will submit a final report with the results, including any publications/abstracts, to the REC.

A copy of all REC reports will be submitted to the Sponsor.

13.2. Peer review

This trial has been funded by Insmed Incorporated who have reviewed the grant application and the protocol has been reviewed and approved by the Sponsor Committee responsible for this.

Resulting publications will be reviewed by the referees of the journal to which the paper will be submitted.

13.3. Public and Patient Involvement

Due to limited time in the development of the protocol, minimal public and patient involvement has been planned in the set-up phase. Lay person review of the PIS, ICF and diary has been completed by the Edinburgh Clinical Research Facility – Covid-19 Patient Public Involvement Advisory Group. Feedback from the group has been adopted throughout these documents. We will involve the European Lung Foundation, a European patient group, in dissemination of research results.

13.4. Regulatory Compliance

The trial will not commence until a CTA is obtained from the Medicines and Healthcare products Regulatory Agency (MHRA) and Favourable REC opinion. The protocol and trial conduct will comply with the Medicines for Human Use (Clinical Trials) Regulations 2004 and any relevant amendments

Before any site can enrol participants into the trial, the CI, PI or delegate will ensure that appropriate approvals from participating organisations are in place.

For any amendment to the trial, the CI, PI or delegate, in agreement with the sponsor, will submit information to the appropriate body in order for them to issue approval for the amendment. The CI, PI or delegate will work with sites (NHS R&D departments at sites as well as the trial delivery team) so they can put the necessary arrangements in place to implement the amendment to confirm their support for the trial as amended.

13.5. Protocol compliance

Prospective, planned deviations or waivers to the protocol are not allowed under the UK regulations on Clinical Trials and must not be used, e.g. it is not acceptable to enrol a participant if they do not meet the eligibility criteria or restrictions specified in the trial protocol. The CI will not implement deviations to the protocol except where necessary to eliminate an immediate hazard to trial participants.

Accidental protocol breaches can happen at any time. They will be adequately documented on the relevant forms and reported to the CI and Sponsor using the TASC Breach Reporting and CAPA Form. In

the event that there is a breach of the protocol, the nature of and reasons for the breach will be recorded in the TMF and documented in the trial TASC Breach Report Log. Breaches from the protocol which are found to frequently recur are not acceptable, will require immediate action and could potentially be classified as a serious breach.

13.6. Notification of Serious Breaches to GCP and/or the protocol

A "serious breach" is a breach which is likely to effect to a significant degree -

- a) the safety or physical or mental integrity of the participants of the trial; or
- b) the scientific value of the trial

The sponsor will be notified immediately of any case where the above definition applies during the trial conduct phase. The sponsor of a clinical trial will notify the licensing authority in writing of any serious breach of

- a) the conditions and principles of GCP in connection with that trial; or
- b) the protocol relating to that trial, as amended from time to time.

If a serious breach of the protocol or GCP is suspected, this will be reported to the Sponsor immediately using the TASC Breach Reporting & CAPA Form and will be recorded in the eCRF and documented in the trial TASC Breach Report Log.

If a breach necessitates a subsequent protocol amendment, this will be submitted to the Sponsor for approval and categorisation and then to the appropriate REC, MHRA and NHS R&D for review and approvals as appropriate.

13.7. Data protection and participant confidentiality

The CI and trial staff will comply with the requirements of the General Data Protection Regulation (EU) 2016/679 (GDPR) and the UK Data Protection Act 2018 or any subsequent amendment or replacement thereof with regard to the collection, storage, processing and disclosure of personal data and will uphold the principles of GDPR in Article 5.

The CI and trial staff will also adhere to the NHS Scotland Code of Practice on Protecting Participant Confidentiality or local equivalent.

All trial records and data will be managed in a manner designed to maintain participant confidentiality. All records, electronic or paper, will be kept in a secure storage area with access limited to appropriate trial staff only. Computers used to collate data will have limited access measures via user names and passwords. Age, gender and ethnicity will be the only personal identifiable details held on CASTOR Electronic Data Capture system.

Personal data or data concerning health will not be released without the existence of a legal basis for processing under Articles 6 and 9 of GDPR, such as official authority 6(1)e or substantial public interest 9(2)g. The CI and trial staff will not disclose or use for any purpose other than performance of the trial, any data, record, or other unpublished, confidential information disclosed to those individuals for the purpose of the trial. Prior written agreement from the Sponsor will be required for the disclosure of any said confidential information to other parties.

Access to collated participant data will be restricted to the CI and appropriate delegated trial staff.

Where data requires to be transferred, an appropriate Data Transfer Agreement will be put in place.

Published results will not contain any personal data that could allow identification of individual participants.

13.8. Financial and other competing interests

The CI has received fees for consulting from the trial funder, Insmed Inc. and holds research grants from Insmed. Any conflict of interest declared by site staff shall be notified to the Sponsor and retained in the TMF.

13.9. Indemnity

The University of Dundee and Tayside Health Board are Co-Sponsoring the trial.

Insurance. – The University of Dundee will obtain and hold Clinical Trials Insurance cover for legal liabilities arising from the trial.

Tayside Health Board will maintain its membership of the Clinical Negligence and Other Risks Insurance Scheme (CNORIS) which covers the legal liability of Tayside in relation to the trial.

Where the trial involves University of Dundee staff undertaking clinical research on NHS participants, such staff will hold honorary contracts with Tayside Health Board which means they will have cover under Tayside's membership of the CNORIS scheme.

Indemnity. The Co-Sponsors do not provide trial participants with indemnity in relation to participation in the Trial but have insurance for legal liability as described above.

Where other Scottish Health Boards are participating as trial sites, those other Scottish Health Boards will maintain membership of CNORIS to cover their liability in relation to their conduct of the trial.

Where other UK NHS organisations are participating as trial sites, those other UK NHS organisations will maintain membership of a scheme similar to CNORIS.

13.10. Amendments

Amendments to protocol will be conducted in compliance with Sponsor SOPs. The decision to amend the protocol will lie with the CI after consultation with the TMG, trial statistician and funder. The CI will seek Sponsor approval for any amendments to the Protocol or other approved trial documents. The Sponsor will decide whether an amendment is substantial or non-substantial. The CI will be responsible for submitting the amendment to the appropriate regulatory authorities and communicating amendments to sites. Amendments to the protocol or other trial documents will not be implemented without approval from the Sponsor and subsequent approval from the appropriate REC and/or MHRA, as appropriate, and NHS R&D Office(s). The amendment history will be detailed in an Amendment Log.

13.11. Post-trial care

As the trial treatment is for a 28 day treatment period only, and if used in clinical care would be a one-off treatment for COVID-19, no advantage is expected from continuing the trial treatment after the initial 28 days. Trial treatment will not be made available to participants at the end of the trial.

13.12. Access to the final trial dataset

The CI and Trial Statistician will have access to the final trial dataset. Access to the final trial dataset to others will be approved by the CI.

14. DISSEMINIATION POLICY

14.1. Dissemination policy

Details of the trial and clinical trial final report will be published on the EudraCT database, the latter no later than 12 months after the end of trial, and will be available to the public via the EU Clinical Trial Register. The report will be made available to the Funder. The report can be used for publication and presentation at scientific meetings. Trial investigators have the right to publish orally or in writing the results of the trial. The criteria for authorship will follow the criteria of the International Committee of Medical Journal Editors.

Publications will be reviewed according to the agreed contractual terms but will not restrict the general rights outlined above for the Investigators to publish the results of the trial.

Summaries of results will also be made available to Investigators for dissemination within their clinical areas (where appropriate and according to their discretion). A newsletter giving a summary of the results of the trial will be made available to participants.

14.2. Authorship eligibility guidelines and any intended use of professional writers

The data arising from this trial resides with the trial team and ownership with the University of Dundee. The criteria for authorship will follow the criteria of the International Committee of Medical Journal Editors. On completion of the trial, the trial data will be analysed and tabulated, and a clinical trial final report will be prepared. The CI will be responsible for authorship of the final report.

16. APPENDICIES

16.1. Appendix 1-Risk

Risks associated with trial interventions							
☐ A ≡ Comparable to the risk of standard medical care							
B ≡ Somewhat high	ner than the risk of standa	ard medical care					
☐ C ≡ Markedly highe	er than the risk of standar	d medical care					
month period in over 2 low risk of adverse effe	n investigational therapy b 200 patients with bronchie ects for 28 days treatmen	ectasis. The treatment t.					
Undesirable effects are	e detailed in section 6.3 o	of the IB					
What are the key risks interventions you plan	related to therapeutic to monitor in this trial?	How will these risks	s be minimised?				
IMP/Intervention	Body system/Hazard	Activity	Frequency	Comments			
Increase in severity of infections	Lung	Close monitoring	as clinically indicated	Not expected in view of phase 2 data			
Hyperkeratosis	Skin	Patients told to report	Daily while in hospital	Rare over 6 months in phase 2			
Dental complications	Teeth	Patients told to report	Daily while in hospital	Not expected with short treatment duration			
Neutropenia	Blood	Regular blood tests	as clinically indicated	Not observed in phase 2 study.			
Outline any other processes that have been put in place to mitigate risks to participant safety (e.g. DMC, independent data review, etc.)							
Participant safety will be reviewed periodically by the DMC.							
An information sheet will be provided for clinical staff caring for the participant detailing dosing instructions and possible adverse effects.							
Outline any processes (e.g. IMP labelling +/- accountability +/- trial-specific temperature monitoring) that have been simplified based on the risk adapted approach. Nil							

16.2. Appendix 2 - Trial management / responsibilities

Responsibilities will be detailed the co-sponsorship and model trial agreements.

16.2.1. Participant registration/randomisation procedure

TCTU TRuST web-based randomisation system will be used: https://hicservices.dundee.ac.uk/TRuST/

Sites will be provided with a randomisation guide detailing the web-based randomisation system process. Prior to recruitment individuals delegated this task and on completion of training will be given a username and password.

16.2.2. Data management

Data management will be overseen by TCTU Data Management Team (DMT).

Local sites will be expected to enter data directly on to the eCRF Worksheets will be provided to facilitate this process but their use is not mandatory. Worksheets, where used, will not record source data and will not be used for monitoring purposes.

All data from participants should be entered on the eCRF within 7 days of the last data collection point for that participant.

Data queries will be generated by the DMT and emailed to sites, return of queries should be within 2 weeks.

16.2.3. Preparation and submission of amendments

TCTU Trial Management Team will be responsible for working with the CI to submit any amendments.

16.2.4. Preparation and submission of Annual Safety Report/Annual

TCTU Trial Management Team will be responsible for liaising with the CI to submit REC annual reports.

The Sponsor Pharmacovigilance Team will be responsible for liaising with the CI to submit Annual Safety Reports.

16.2.5. Data protection/confidentiality

The CI and trial staff will comply with the requirements of the EU General Data Protection Regulation and the Data Protection Act 2018 or any subsequent amendment or replacement thereof with regard to the collection, storage, processing and disclosure of personal data and will uphold the Principles of GDPR in Article 5.

The CI and trial staff will also adhere to the NHS Scotland Code of Practice on Protecting Participant Confidentiality or local equivalent.

16.2.6. Trial documentation and archiving

Archiving trial site data will be the responsibility of individual sites. Payment for archiving will be provided as per site agreement.

16.3. Appendix 3 – Authorisation of participating sites

16.3.1. Required documentation

The following data should be made available to TCTU Trial Management Team prior to site initiation:

- PI CV, signed and dated
- PI GCP certificate
- · Protocol signature page, signed and dated by PI
- Copy of signed Participating Site Agreement
- Copy of R&D confirmation of capacity and capability

The following data should be made available and held within the ISF/PSF prior to site initiation:

- CV, signed and dated for all trial staff listed on Delegation Log
- GCP certificate for all trial staff listed on Delegation Log

16.3.2. Procedure for initiating/opening a new site

Site Initiation will be carried out remotely due to COVID-19 pandemic.

Site Initiation will be performed by Sponsor monitors and TCTU Trial Management Team.

TCTU Trial Management Team will initiate release of trial drug to the site after R&D confirmation of capacity and capability.

16.3.3. Principal Investigator responsibilities

The PI's legal responsibilities will be listed in the Participating Site Agreement a summary is given below:

- Attendance at the initiation teleconference,
- Training of new members of trial staff in the protocol and its procedures,
- · Ensuring that the ISF is accurately maintained,
- Dissemination of important safety or trial related information to all stakeholders within their site
- Safety reporting within the required timelines
- Ensuring data entry to eCRF and responses to data clarification queries are completed within the required timelines.
- Certify data entered on eCRF is correct and complete.
- Ensuring any trial staff coming into contact with participants have the appropriate Personal Protective Equipment and training in its use.
- · Archiving of site trial data.

16.4. Appendix 4 – Schedule of Procedures

	Screeningd	Randomization ^d			Follow-up Assessments	Follow-up assessments	Follow-up Assessments	Unscheduled Assessments
Timeline	Day 0 or 1	Day 1 Up to 24 hours after screening	Daily whilst hospitalised	Days 3, 5 &11 ° (telephone call if at home)	Day 8° (telephone call if at home)	Day 15 ° (telephone call if at home)	Day 29 ^c (telephone call if at home ^b)	As Required in the event of AE
Informed Consent	Х				,			
Inclusion/Exclusion Criteria Check	Х	Х						
Medical History	Х							
Record Concomitant Medications	Х	Х			Х	Х	Х	Х
Check Vital Signs*^	Х	Х			X∞	X∞	X∞	X
ECG*	Х							
Full blood count*+	Х			X∞	Х∞	X∞	X∞	
Urea and electrolytes*+	Х			X∞	X∞	X∞	X∞	
Liver function tests*+	Х			X∞	X∞	X∞	X∞	
SARS CoV-2 PCR*	Χ							
Record SARS CoV-2 PCR results, only if done for clinical reasons				×	X	×	×	
Nasal swab for SARS CoV-2 PCR* (Tayside only)						X∞	Х	
Research Blood Sample * (Tayside and Sheffield only)		X			X∞	X∞	X	Х
Sputum sample for storage if available*+ (Tayside only)		X			X∞	X∞	Х	
Endotracheal aspirate sample for storage if available*+a (Tayside only)					X∞	X∞	X∞	
Clinical status on 7 point scale	Х	Х	Х	Х	Х	Х	Х	Х
NEWS recording*	Х	Х	Х	X∞	X∞	X∞	X∞	

	Screening ^d	Randomization ^d			Follow-up Assessments	Follow-up assessments	Follow-up Assessments	Unscheduled Assessments
Timeline	Day 0 or 1	Day 1 Up to 24 hours after screening	Daily whilst hospitalised	Days 3, 5 &11 ° (telephone call if at home)	Day 8° (telephone call if at home)	Day 15 ^c (telephone call if at home)	Day 29 ° (telephone call if at homeb)	As Required in the event of AE
EQ-5D questionnaire							Х	
Record supplemental oxygen*	Х	Х			X∞	X∞	X∞	Х
Record CT scan results, only if done for clinical reasons	Х	Х	Х	X∞	X∞	X∞	X∞	X∞
Pregnancy Testing (urine or blood) If Applicable	Х							
Record Adverse Events		X	Х	Х	Х	Х	Х	Х
Randomisation		X						
Dispense Trial Drugs		Χ						
Drug Return And Compliance Check							X	

[^] Vital Signs: Blood Pressure, pulse, temperature, oxygen saturation

^{*}indicates procedures that will be performed by the clinical team as part of routine care but results will be recorded and included in the eCRF. If not performed by the clinical team, but clinically indicated, the research team may assist in this being performed but all processes will avoid duplication and exposure to potentially infected participants.

⁺Excess biological samples that are being taken for clinical reasons may be stored for future use if no longer required for clinical purposes (Tayside only).

^a For those participants who are intubated.

[∞]These assessments will not be completed if the participant has been discharged from hospital.

^b For the Tayside and Sheffield site only, the day 29 assessments will be carried out face-to-face either at a NHS facility or at the participant's home. Home visits will only be carried out if no one in the household has symptoms of COVID-19.

^cResearch blood samples (Tayside and Sheffield only) and, once discharged, assessments may be completed within +/- 1 day

^dScreening and randomisation may occur on the same day if all eligibility criteria are met. Day of first dose of IMP will be considered as day 1 for the calculation of follow up assessments.

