3.7. Table of endpoints/outcomes

Objectives	Outcome Measures	Timepoint(s)
Primary Objective Participant clinical status (on a 7- point ordinal scale) In accordance with WHO recommendations the primary endpoint will be determined by a pilot trial of the first 100 participants.	 7-point ordinal scale: Not hospitalised, no limitations on activities Not hospitalised, limitation on activities; Hospitalised, not requiring supplemental oxygen; Hospitalised, requiring supplemental oxygen; Hospitalised, on non-invasive ventilation or high flow oxygen devices; Hospitalised, on invasive mechanical ventilation or ECMO (Extracorporeal membrane oxygenation) Death. 	Up to day 29
Secondary Objectives	Outcome Measures	Timepoint(s)
Evaluate the clinical efficacy of Brensocatib relative to standard care in adult patients hospitalised with COVID-19	Clinical Severity Time to an improvement of one category from admission using 7-point ordinal scale. Participant clinical status on 7-point ordinal scale Mean change in the 7-point ordinal scale	Daily whilst hospitalised Days 3, 5, 8, 11, 15 and 29. Baseline to days 3, 5, 8, 11, 15 and 29.
	National Early Warning Score (NEWS): Time to discharge or to a NEWS of ≤ 2 and maintained for 24 hours, whichever occurs first. Change from baseline Oxygenation:	Daily whilst hospitalised Days 8, 15, 29
	Oxygen free days Incidence and duration of new oxygen use during the trial	1-29 days 0-29 days
	Mechanical Ventilation: Ventilator free days	1-29 days

	Incidence and duration of new mechanical ventilation use during the trial.	1-29 days
	Hospitalisation:	
	Duration of hospitalisation (days).	Date of admission and discharge
	Mortality:	
	28-day mortality	Date of death
Evaluate the safety of the	Cumulative incidence of SAEs	1-29 days
intervention through 28 days of follow-up as compared to the control arm	Discontinuation or temporary suspension of treatment	1-29 days
	Changes in white cell count, haemoglobin, platelets, creatinine, total bilirubin, ALT, and AST over time (hospitalised participants only)	Days 0/1, 3, 5, 8, 11, 15, 29
	Adverse events of special interest- hyperkeratosis, infections and dental complications	1-29 days
	dental complications	
Exploratory Objectives	Outcome Measures	Timepoint(s)
Exploratory Objectives Evaluate the virologic efficacy of Brensocatib	·	Timepoint(s) Day 15 and day 29

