It is expected that these clinical assessments will be carried out by the clinical team during routine clinical care and documented on a NEWS chart. Where the assessments have been carried out, the results of the assessment closest to 8am on the day will be used to prevent duplication and further exposure of the trial staff to patients with COVID-19.

- Blood pressure and pulse, lying or seated
- Tympanic temperature
- SpO2
- Record if SpO2 has been measured on air or oxygen concentration the participant was receiving.

Ordinal Scale

The ordinal scale is an assessment of the clinical status on a given trial day. Each day, the worst score for that day will be recorded. The scale is as follows:

- 1. Not hospitalised, no limitations on activities
- 2. Not hospitalised, limitation on activities;
- 3. Hospitalised, not requiring supplemental oxygen;
- 4. Hospitalised, requiring supplemental oxygen;
- 5. Hospitalised, on non-invasive ventilation or high flow oxygen devices;
- 6. Hospitalised, on invasive mechanical ventilation or ECMO;
- 7. Death.

NEWS Score

The NEWS score has demonstrated an ability to discriminate patients at risk of poor outcomes. (Smith, 2016). This score is based on 7 clinical parameters. The NEWS2 Score is being used as an efficacy measure.

This should be evaluated at the assessment recorded closest to 8am on a given trial day. These parameters can be obtained from the hospital chart.

Exploratory assessment- viral shedding

Where practical at the Tayside site only, nasal swabs will be obtained on day 15 and day 29 to evaluate viral clearance by PCR.

Exploratory assessment- neutrophil studies

At the Tayside and Sheffield sites only, additional blood will be taken for isolation of peripheral blood neutrophils, as per outcome measures section 3.7.

Exploratory assessment- quality of life

The validated EQ-5D-5L quality of life tool will be administered to patients who are able to complete the questionnaire either in person (those still in hospital) or over the telephone (those at home) to determine the impact of treatment on quality of life.

Clinical Evaluation

As these participants are in-patients receiving care for COVID-19, they will be monitored as per clinical need. Where already obtained for clinical need the following blood results will be recorded at days 1, 3, 5, 8, 11, 15, 29:

- White cell count, haemoglobin, platelets, neutrophils, eosinophils, lymphocytes
- creatinine, eGFR
- AST and ALT

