## 9.2.6 No of days free from oxygen

Number of days free from oxygen support will be compared between the treatment arms using the negative binomial regression with time in ICU as the offset. Number of days will be calculated as the number of days free from oxygen support reported on the 7-point ordinal scale eCRF.

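### Home oxygen has no scheduled record after discharge, so oxygen-free days and duration of new oxygen cannot be measured over the day 29 window set for them

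*Protocol*

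**What the plan says.** Protocol 3.7 lists "Oxygen free days" over days 1-29 and "Incidence and duration of new oxygen use during the trial" over days 0-29. Neither window is limited to the hospital stay.

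In Protocol 16.4 the row "Record supplemental oxygen" is filled at screening, at randomisation, at days 8, 15 and 29, and at unscheduled visits. The three follow-up entries carry the ∞ mark, explained as: "These assessments will not be completed if the participant has been discharged from hospital". SAP Table 1 repeats the row and the footnote.

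The 7-point scale (Protocol 7.8, SAP 4.3) continues by telephone after discharge. Its home categories are "Not hospitalised, no limitations on activities" and "Not hospitalised, limitation on activities". Supplemental oxygen first appears in category 4, "Hospitalised, requiring supplemental oxygen".

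SAP 9.2.6 gives the derivation of oxygen-free days: "Number of days will be calculated as the number of days free from oxygen support reported on the 7-point ordinal scale eCRF". SAP 9.2.7 says that duration of new oxygen will be calculated, but names no data source.

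**The concern.** A participant who goes home on oxygen and one who goes home without it can receive the same scale score on every later day, and no scheduled form separates them. If home days then count as oxygen-free, discharge on oxygen looks like coming off oxygen, and a real reduction in home oxygen goes unseen.

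This bears on a stated aim. Fewer days dependent on oxygen is part of the trial hypothesis (Protocol 1, SAP 3.1), and needing supplemental oxygen is one of the qualifying criteria (Protocol 6.1). Days at home are also likely to make up much of the window: the planning distribution in Protocol 10.1, Table 4 puts 42% + 38% = 80% of controls out of hospital at the endpoint.

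**Working it through.** No stated figure depends on this point, so there is none to reproduce. The check compares passages; an illustrative size follows.

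**1. Is there a scheduled oxygen record after discharge?**
- Oxygen row: ∞ at days 8, 15 and 29, so no. It is blank at days 3, 5 and 11.
- NEWS, which has an air-or-oxygen item (SAP 4.3): ∞ at every follow-up day, so no.
- 7-point scale: collected at the calls on days 3, 5, 8, 11, 15 and 29, but categories 1 and 2 do not refer to oxygen.
- Missing status in a discharged, living participant: SAP 7.4 assigns category 2, which again carries no oxygen information.

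**2. What does SAP 9.2.6 do with home days?** The scale is scored daily only in hospital, and no rule covers the days between calls. Take a participant who leaves hospital on day 8 on oxygen and uses it through day 29. Day 8 is scored in hospital on its worst value, so the home days number 29 − 8 = 21, all on oxygen.

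| Reading of SAP 9.2.6 | Home days counted oxygen-free | True number |
|---|---|---|
| Every home day takes its home category | 21 | 0 |
| Only call days count (11, 15, 29) | 3 | 0 |
| Home days are not counted | 0, but the endpoint ends at day 8 | 0 |

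The first reading is the natural one for a days 1-29 endpoint. The first two misclassify home-oxygen days. The third avoids that but no longer covers the window in Protocol 3.7.

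**3. New oxygen.** Oxygen started in hospital is seen on the daily scale, so its incidence is captured before discharge. Only oxygen first started at home is missed. Duration is cut short at discharge unless some other source is used, and SAP 9.2.7 names none.

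**4. Illustrative size (rates and durations are assumptions).**

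Mean overcount per participant = share on home oxygen × home-oxygen days each.
- Low: 0.05 × 7 = 0.35 days
- High: 0.20 × 14 = 2.8 days

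If the share is instead applied to the 80% at home in Table 4, with wider limits:
- Low: 0.80 × 0.01 × 7 = 0.056 days
- Middle: 0.80 × 0.05 × 14 = 0.56 days
- High: 0.80 × 0.20 × 21 = 3.36 days

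These are shifts in the mean, and they would arise in both arms. A between-arm error needs the arms to differ. For example, shares of 10% and 5% would give (0.10 − 0.05) × 7 = 0.35 to (0.10 − 0.05) × 14 = 0.70 days, in either direction depending on which arm has the larger share.

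**The case against.** - **No sentence says that home days are oxygen-free.** This stands as a limit. A reader might infer a written misclassification rule, but the SAP gives no rule for days after discharge, and its use of ICU time as an offset makes the intended day count less clear. The point does not depend on such a rule, because the information needed to classify those days is not scheduled to be collected.
- **Some home oxygen may be captured elsewhere.** Unscheduled visits for adverse events have an oxygen entry without the ∞ mark, concomitant medications are recorded at days 8, 15 and 29 without it, and SAP 7.4 refers to linked routine records. It would therefore be too strong to say that oxygen can never be recorded after discharge. However, nothing feeds these sources into the oxygen endpoints, and SAP 9.2.6 names only the scale form.
- **The treatment comparison need not be biased.** This stands. A reader might infer that earlier discharge on oxygen favours the drug, but in a randomised, double-blind trial an overcount of equal size in both arms leaves the difference in mean days unchanged. The documents give no basis for a size or a direction.
- **Incidence of new oxygen is mostly safe.** This stands, apart from oxygen first started at home.
- **Only secondary endpoints are touched.** This stands. Oxygen-free days are not among the key secondary endpoints in SAP 7.6.
- **It may be too late to add a question.** SAP version 2 is dated 05-04-2021 and the protocol expected recruitment to end by January 2021, so the calls may already be complete. That limits the remedy but does not remove the gap.

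**Conclusion.** The point holds for secondary endpoints. Oxygen-free days and duration of new oxygen are set over windows ending at day 29, but the scheduled oxygen record stops at discharge and the scale used for oxygen-free days cannot show home oxygen. On the natural reading, each home-oxygen day adds one false oxygen-free day.

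The average overcount is unknown. The 0.35 to 2.8 days per participant rests on an assumed 5% to 20% of participants with 7 to 14 days each; the wider assumptions give about 0.06 to 3.4 days. These figures show scale only and are not estimates of bias in the treatment effect.

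A reader might go further and doubt the main result. The documents do not support that: the primary endpoint is the scale itself at day 29, and neither it nor the sample size uses home oxygen.

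**What to change.** **Participants still in follow-up.** At the calls already scheduled for days 3, 5, 8, 11, 15 and 29, ask whether oxygen is used at home and record start and stop dates. Amend the Schedule row to match. In SAP 9.2.6 and 9.2.7, count those days as oxygen days and name the data source. The cost is one question and a small addition to the eCRF. The downside is recall error, greatest over the 29 − 15 = 14 days between the last two calls.

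**Participants whose calls are complete.** State in the SAP how days after discharge are classified, and label the endpoints as in-hospital oxygen use. This needs only text, but the endpoints then no longer describe the whole window in Protocol 3.7, and the report should say so. If concomitant-medication or linked records turn out to hold home oxygen, a sensitivity analysis could use them.
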